#### Skin

# Skin Adverse Event Management Algorithm

Rule out non-inflammatory causes. If non-inflammatory cause, treat accordingly and continue I-O therapy.

[figure not shown]

Patients on IV steroids may be switched to an equivalent dose of oral corticosteroids (e.g. prednisone) at start of tapering or earlier, once maximized climical improvement is observed. Lower bioaxisliability of oral corticosteroids should be taken into account when switching to the equivalent dose of oral corticosteroids. "Refer to IICI CTCAE v4 for berm-specific grading criteria.

# **Nervous system**

# **Neurological Adverse Event Management Algorithm**

Rule out non-inflammatory causes, if non-inflammatory cause, treat accordingly and continue I-O therapy.

Patients on IV steroids may be switched to an equivalent dose of oral corticosteroids (e.g. prednisone) at start of tapering or earlier, once sustained clinical improvement is observed. Lower bioavailability of oral corticosteroids should be taken into account when switching to the equivalent dose of oral corticosteroids.

# APPENDIX 4 Procédure SPILF - COREB - Vaccine

For French sites: The infectious disease unit of the hospital/infectious reference site must be involved in case of suspicion of a VV-related serious complication.

#### Procédure SPILF - COREB - Vaccine

Comment prendre en charge un patient suspect d'infection par le virus de la vaccine ?

En contexte d'utilisation de thérapies oncolytiques ayant pour support un virus de la vaccine génétiquement modifié, cette procédure résumée est destinée aux soignants de 1 ète ligne prenant en charge un patient suspect de vaccine. A ce jour sur 300 patients traités, 20% ont présenté une éruption cutanée pustuleuse limitée en taille (< 1 cm) ou muqueuse dans les 7 jours après injection, résolutive sans complications en 3 semaines.

Compte-tenu des complications possibles de ces traitements, de la potentielle transmission par contact, il est essentiel que les cancérologues référents de ces patients qui dépistent un patient suspect de vaccine 1) appellent rapidement l'expertise infectiologique, et 2) qu'une protection adaptée soit proposée au patient et aux soignants.

1- DEPISTER - Patient suspect = Tableau clinique, 7 à 14 jours après exposition ET Exposition compatibles. Tableau clinique le plus évocateur : éruption de lésions cutanées pustuleur es (photo) de taille <1 cm en nombre limité < à 5, voire érosions muqueuses buccales, ayant évolué d'un

aspect de papules érythémateuses, à celui de vésicules à liquide trouble, puis pustules, puis croutes

- Fièvre possible - Aspects atypiques à ne pas exclure sans analyse experte, si exposition caractérisée Exposition : injection intra-lésionnelle ou parentérale de virus de la vaccine

modifié à visée oncolytique (Pexa vec ou TG 6002); ou contact proche avec un patient cas possible ou documenté, ou accident d'exposition au produit oncolytique.

Analyse clinique experte pour estimer la probabilité diagnostique après exposition

- Patient suspect : manifestations non évocatrices, diagnostic alternatif possible à documenter, PCR en attente
- Cas possible : manifestations évocatrices, PCR en attente
- Cas confirmé: manifestations compatibles, PCR positive dans le sang ou prélèvement local
- Cas exclu : manifestations non évocatrices et PCR négative dans le sang et prélèvement local.
   Diagnostic alternatif : évoquer et documenter (PCR à partir des lésions) une autre infection virale à Herpes virus (HSV, varicelle-zona) ou autres (pox) virus, pouvant prendre des aspects atypiques chez ces patients ayant reçu des chimiothéraples possiblement immunosuppressives. Dermite ou eczéma de contact, érythème
- 2- PROTEGER, des la suspicion, et jusqu'à infirmation du diagnostic

polymorphe, toxidermies bulleuses, autres dermatoses vésiculo-pustuleuses

- > Patient : isolement en chambre seule, SHA, port de masque chirurgical (si lésions buccales), lésions cutanées couvertes (pansement non compressif) jusqu'à la chute des croutes.
- > Soignant : Application stricte des précautions standard et complémentaires de type contact avec surblouse usage unique, port de gants (masque chirurgical si lésion buccale chez le patient).
- Gestion des déchets de soins : prévoir une filière spécifique risque infectieux avec incinération (DASRI).
- Identification (précoce) des personnes contact. Prévention AES : soignants informés.

# 3- PRENDRE EN CHARGE

· Recherche de signes et facteurs de gravité :

vaccine sur prélèvement cutanéo-muqueux et sanguin.

Signes de gravité spécifiques (extension de l'éruption, sepsis, manifestations neurologiques ont été décrits après vaccination antivariolique, non décrits à ce jour dans le contexte de thérapies oncolytiques. Prise en compte d'éventuelles co-morbidités (eczêma et autre dermatose inflammatoire chronique).

- Traitement au plus tôt, au minimum symptomatique. Contre-indication : aux AINS, et aux anticoagulants. Indications traitements spécifiques : dépendent du type, nombre, extension des lésions, signes systémiques, et évolutivité des manifestations. Avec expertise clinique infectiologique, et RCP, associant les industriels responsables de leur délivrance autant que de besoin.
- Modalités traitements spécifiques : durée à titre indicatif, 14j, adaptée selon évolution
- Immunoglobulines spécifiques anti-virus vaccine : 6000 à 9000 Ul/kg en une perfusion lente (2 ml/minute) sur une voie d'abord spécifique : à renouveler selon évolution clinique
- Brincidofovir: 4 mg/kg chez les patients de moins de 50 kg, et 200 mg si plus de 50 kg, PO, une fois par semaine Surveillance de la tolérance gastro-intestinale (diarrhées graves décrites) et rénale
- Alerte et Orientation du patient : Dès la suspicion de vaccine, appel de l'infectiologue référent pré-identifié (cf infra) pour expertise en vue de prise en charge ; et, si cas confirmé, pharmacovigilance, ANSM - si patient cas possible ou confirmé : transfert en service MIT, structure de traitement dédié
- si patient suspect : discussion /expertise clinique et prise en compte des diagnostics alternatifs Confirmation virologique dès que possible, par le laboratoire référent. Mesures d'hygiène et biosécurité (guide OMS) pour prélèvements, leur transport et manipulations à visée diagnostic, y compris alternatif. PCR

 
Infectiologue référent /
 
	ESR à joindre : Nom :	Téléphone :

# **APPENDIX 5**

# Instructions for VIG medication ordering and shipment

Vaccinia Immune Globulin (VIG) will be provided to the Investigator and Pharmacist through the process described hereafter.

The site should contact immediately:

# Emergency 24/7 telephone number (any country):

and will complete and send a "Notification of VIG Medication Request Form"

VIG will be shipped as soon as possible from the central depot to the patient's treating facility.

Upon reception of VIG, follow the instructions in VIG Summary of Product Characteristics.

For France, the instructions of the SPILF-COREB Vaccine procedure for the dosage treatment (see APPENDIX 4) should be followed.

## LIST OF ABBREVIATIONS

AE Adverse Event

AFP Alpha-Foetoprotein

BCLC Barcelona Clinic Liver Cancer

BMI Body Mass Index
bpm Beats per minute
CI Confidence Interval
CR Complete Response

CRF Case Report Form

CRO Contract Research Organization

CS Clinically significant

CTCAE Common Terminology Criteria for Adverse Events

DCR Disease Control Rate
DLT Dose Limiting toxicity
DoR Duration of Response

eCRF Electronic Case Report Form

EOT End of Treatment
EOS End of Study

ETOH Ethanol

HBV Hepatitis B Virus

HCC Hepatocellular Carcinoma

HCV Hepatitis C Virus

HR Hazard Ratio

ICF Informed Consent Form

IMP Investigational Medicinal Product

INT Integer part
IT Intratumoral
ITT Intent To Treat
IU International Unit

ISC Independent Safety Committee

IV Intravenous

LLN Lower Limit of Normal

MH Medical History

MIN Minimum

| MAX      | Maximum                                      |
|----------|--|
| N        | Number                                       |
| NA       | Not Applicable                               |
| NASH     | Non-Alcoholic Steato Hepatitis               |
| NCI      | National Cancer Institute                    |
| NCS      | Not Clinically Significant                   |
| ORR      | Overall Response Rate                        |
| OS       | Overall Survival                             |
| PD       | Progressive Disease                          |
| PFS      | Progression Free Survival                    |
| PP       | Per Protocol                                 |
| PR       | Partial Response                             |
| PT       | Preferred Term                               |
| RECIST   | Response Evaluation Criteria In Solid Tumors |
| SAE      | Serious Adverse Event                        |
| SAF      | Safety                                       |
| SC       | Subcutaneous                                 |
| sd       | Standard deviation                           |
| SD       | Stable Disease                               |
| SI units | International System of units                |
| SOC      | System Organ Class                           |
| TTP      | Time To Progression                          |
| ULN      | Upper Limit of Normal                        |

#### 1 UPSTREAM DOCUMENTATION

The following documents were used to prepare the Statistical Analysis Plan:

- Study protocol TG6006.01 Version dated 22 December 2017
- eCRF Version 6.0 dated 16 February 2018

#### 2 STUDY DESIGN

This is an open-label single-arm Phase I/IIa study.

## 2.1 Phase I

The Phase I part is a single cohort enrolling 6 patients at standard Pexa-Vec and nivolumab doses, i.e.  $1x10^9$  pfu and 240 mg, respectively.

Pexa-Vec will be administered by intra-tumoral infusion on D1, D15 and D29, and nivolumab by intravenous infusion on D15 and D29 and then every two weeks. The study will document dose-limiting toxicities (DLTs) and landmark AEs. A landmark AE is an anticipated effect of the combination defined as an increase in severity of hepatic cytolysis (doubling of AST – ALT baseline blood concentrations), or significant deterioration of hepatic function (INR, bilirubin), or increase in incidence or severity of immune-related AEs, or increase in number or severity of Pexa-Vec-related skin lesions.

The first patient will be monitored for the safety scheduled up to D29, i.e. the end of the DLT monitoring period, before 5 additional patients can be enrolled. In addition, a security time interval of 2 weeks between enrolments of consecutive patients will apply. This time interval is appropriate to prevent additional patients to be exposed to potential acute or subacute toxic events observed in the previous patients.

If more than one DLT is observed in the first 6 patients, or in case of the occurrence of a landmark AE, one de-escalation dose regimen will apply on a cohort of 6 additional patients. Depending on the DLT profile relative to the known toxicity of each component of the combination and upon the recommendation of the Independent Safety Committee (ISC), the doses of Pexa-Vec and nivolumab will be either  $3x10^8$  pfu for Pexa-Vec and 240 mg q2 weeks for nivolumab OR  $10^9$  pfu for Pexa-Vec and 240 mg q3 weeks for nivolumab

In case no more than one DLT and no occurrence of any landmark AE is observed in 6 patients at the initial Phase I dose level or, if relevant, at the de-escalation dose level, the Phase IIa part of the study could start.

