#### 6 TREATMENT PLAN

#### 6.1 Treatment administered

### 6.1.1 Treatment regimens

### 6.1.1.1 Phase I part:

Safety and efficacy will be assessed in 6 patients, using a standard regimen for dose level 1 as 3 bi-weekly IT injections of 1x10^9 pfu for Pexa-Vec and 240 mg IV q2weeks for nivolumab (Figure 1: IMP administration scheme).

In case of a Dose-Limiting Toxicity (DLT) is observed in more than one patient out of the first 6 patients, or in the occurrence of a landmark AE, one de-escalation regimen is planned:

• Dose level -1: 3 bi-weekly IT injections of 3x10^8 pfu for Pexa-Vec and 240 mg q2weeks for nivolumab OR 3 bi-weekly IT injections of 10^9 pfu for Pexa-Vec and 240 mg q3 weeks for nivolumab, depending on the DLT profile relative to the known toxicity of each component of the combination, as judged by the Independent Safety Committee (ISC).

A landmark AE is an anticipated effect of the combination, defined as either increase in severity of hepatic cytolysis (doubling of AST – ALT baseline blood concentrations), or significant deterioration of hepatic function (INR, bilirubin), or increase in number or severity of immunerelated AEs, or increase in number or severity of Pexa-Vec-related skin lesions.

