# 6.2 Recommended Phase II dose (RP2D)

In the Phase I part, all patients will be monitored up to D29 for the occurrence of DLTs that defines the DLT period. The RP2D is defined as the maximum dose level (1 or -1) at which a DLT attributable to the IMPs is observed at most in one patient out of 6 patients in the DLT period and upon final recommendation of the ISC that will prevail.

The **DLTs**, applicable for the Phase I part of the study, are defined as such:

- 1. All Grade 3-4 non-hematologic toxicity that represents a 2-grade increase over baseline, excluding:
  - Untreated or inadequately treated nausea, vomiting and diarrhea,
  - Untreated or inadequately treated fever > 40.0°C lasting less than 24 hours (Grade 3); only fever > 40.0°C lasting more than 24 hours (Grade 4) qualifies for DLT,
  - Alopecia,
  - Grade 3 fatigue that returns to grade 2 or less within 7 days,
  - Grade 3 laboratory/metabolic abnormalities, other than ALT or AST, that are not considered clinically significant and that return to grade 2 or less within 72 hours.
- 2. Any Grade ≥ 3 treatment-related acute immune-related AE involving major organs, such as: immune-related pneumonitis, colitis, nephritis, hepatitis, endocrinopathies, immune-related rash and other rare but severe immune-related reactions.
- 3. Grade  $\geq$  3 injection site reaction.
- 4. AST or ALT  $\geq$  10xULN, even if asymptomatic, unless it is related to a definite progression of liver metastases or another clearly identifiable etiology; doubling of AST or ALT that is concurrent with a doubling of the total bilirubin.
- 5. Any toxicity at least possibly related to study therapy that results in a delay in treatment of 2 or more weeks.
- 6. Hematological:
  - Grade ≥ 3 or ≥ 2-grade increase over baseline of neutropenia lasting for more than 7 days.
  - Neutropenic fever.
  - Grade 4 thrombocytopenia or grade 3 thrombocytopenia with clinically significant bleeding.
- 7. Cardiac: association of the 3 following cardiac abnormalities
  - Left ventricular ejection fraction (LVEF) less than the lower limit of normal (LLN), as
    assessed by echocardiography and symptomatic due to drop in ejection fraction,
    responsive to intervention,
  - Increase of blood troponin T or I above the upper limit of normal (ULN),
  - Any ECG abnormality consistent with a Grade 3 cardiac disorder.

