# 6.3 Method of assigning patients to treatment groups

#### 6.3.1 Recruitment

The study involves one group of patients, distributed in consecutive cohorts, Phase I dose-level 1 and -1, and Phase IIa.

The Investigator will be asked to complete a "screening log" in which each potential patient (i.e. screened patient) will be listed. After having signed the informed consent form, a screened patient is considered as a "consented patient".

Upon satisfaction of all of the inclusion and exclusion criteria for a "consented patient", the patient will be considered as an "eligible patient" for the study. This process is fully documented on the "screening log" should a patient be included or not in the study.

In Phase I, the first enrolled patient will be monitored for safety up to the completion of 3 Pexa-Vec IT injections and 2 nivolumab infusions, scheduled on D29 (i.e. week 4), before the second patient can be enrolled. A security interval of 2 weeks between enrolments of each consecutive patients will be applied. In case of occurrence of a DLT in more than one patient in the first cohort of 6 patients treated at Dose-Level 1, another cohort of 6 patients will be enrolled, who will be treated at the dose de-escalation level (-1).

In Phase IIa, patients will be enrolled without security intervals between consecutive patients.

Under no circumstances will a patient enrolled in the study be permitted to re-enroll for a second time in the study.

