## **Discontinuation Criteria**

Treatment should be permanently discontinued for the following (applicable for Phase I and Phase II parts of the study):

- Any Grade 2 drug-related uveitis or eye pain or blurred vision that does not respond to topical therapy and does not improve to Grade 1 severity within the re-treatment period OR requires systemic treatment
- Any Grade 3 non-skin, drug-related adverse event lasting > 7 days, with the following exceptions for drug-related laboratory abnormalities, uveitis, pneumonitis, bronchospasm, hypersensitivity reactions, and infusion reactions, and endocrinopathies:
  - o Grade 3 drug-related uveitis, pneumonitis, bronchospasm, hypersensitivity reaction, or infusion reaction of any duration requires discontinuation
  - o Grade 3 drug-related endocrinopathies adequately controlled with only physiologic hormone replacement do not require discontinuation
  - o Grade 3 drug-related laboratory abnormalities do not require treatment discontinuation except those noted below
- Grade 3 drug-related thrombocytopenia > 7 days or associated with bleeding requires discontinuation
- Any drug-related liver function test (LFT) abnormality that meets the following criteria require discontinuation:
  - o AST or ALT  $> 8 \times ULN$
  - o Total bilirubin > 5 x ULN
  - Concurrent AST or ALT > 3 x ULN and total bilirubin > 2 x ULN
- Any Grade 4 drug-related adverse event or laboratory abnormality, except for the following events which do not require discontinuation:
  - Isolated Grade 4 amylase or lipase abnormalities that are not associated with symptoms or clinical manifestations of pancreatitis and decrease to < Grade 4 within 1 week of onset.
  - Isolated Grade 4 electrolyte imbalances/abnormalities that are not associated with clinical sequelae and are corrected with supplementation/appropriate management within 72 hours of their onset
  - Grade 4 lymphopenia or leucopenia
  - Grade 4 drug-related endocrinopathy adverse events, such as adrenal insufficiency, ACTH deficiency, hyper- or hypothyroidism, or glucose intolerance, which resolve or are adequately controlled with physiologic hormone replacement (corticosteroids, thyroid hormones) or glucose-controlling agents, respectively, may not require discontinuation after discussion with and approval from the Coordinating Investigator [as allowed by protocol].
  - Any dosing interruption lasting > 6 weeks with the following exceptions:

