#### 7.2 ISC for Phase I

ISC will review safety data when 6 evaluable patients for Phase I have reached their Day 29 visit:

- In case no more than 1 Dose-Limiting Toxicity (DLT) is observed in 6 patients and no occurrence of any landmark AE (see section 2.1), then accrual in the Phase IIa part of the study will start at the same dose level.
- In case of more than one DLT is observed, or the occurrence of a landmark AE, one deescalation regimen is planned to Level -1, depending on the DLT profile relative to the known toxicity of each component of the combination, as judged by the ISC:
  - o 3 bi-weekly IT injections of 3x10^8 pfu for Pexa-Vec and 240 mg q2 weeks for nivolumab OR
  - o 3 bi-weekly IT injections of 10^9 pfu for Pexa-Vec and 240 mg q3 weeks for nivolumab.

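### Phase I dose decision: the protocol counts patients with a DLT, the SAP counts DLTs, and the protocol contradicts itself on whether a patient stopped by a DLT is evaluable

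*SAP*

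**What the plan says.** **Counting unit.** The protocol counts patients wherever it states the rule. Section 6.1.1.1 reads "In case of a Dose-Limiting Toxicity (DLT) is observed in more than one patient out of the first 6 patients", and 6.3.1 reads "In case of occurrence of a DLT in more than one patient in the first cohort of 6 patients treated at Dose-Level 1". Section 6.2 defines the recommended Phase II dose as the highest level at which "a DLT attributable to the IMPs is observed at most in one patient out of 6 patients in the DLT period". Section 3.1.1 and the synopsis use the same unit.

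The SAP counts DLTs, in both directions. To de-escalate, SAP 2.1 says "If more than one DLT is observed in the first 6 patients, or in case of the occurrence of a landmark AE" and SAP 7.2 says "In case of more than one DLT is observed, or the occurrence of a landmark AE". To proceed, SAP 2.1 says "In case no more than one DLT and no occurrence of any landmark AE is observed in 6 patients".

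**Who is evaluable for Phase I.** The protocol's Definitions table and section 12.6 require completion of the DLT period with all three Pexa-Vec injections and both nivolumab infusions. The DLT population in protocol 12.6 is built on that definition. Protocol 6.6.2, SAP 2.3 and the DLT population in SAP 6.1 accept either completion or a DLT. SAP 6 names the DLT population as the basis for the de-escalation decision.

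**Deviations.** Protocol 12.5 lists Phase I non-completion as a major deviation leading to replacement, with no exception for a DLT. SAP 6.2 lists the same deviation but exempts patients with a DLT.

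**The concern.** A dose-decision threshold and a safety analysis set should each have one definition. On the first point, the two documents can send the same six patients to different decisions. On the second, a completers-only set is wrong in principle for counting DLTs: a DLT is often the reason a patient does not complete, so the set can lose the patients it exists to count.

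This can happen under the protocol's own rules. Among the DLTs in section 6.2 is "Grade 4 thrombocytopenia or grade 3 thrombocytopenia with clinically significant bleeding". Under 6.3.4.2, "Grade 3 drug-related thrombocytopenia > 7 days or associated with bleeding requires discontinuation". A patient with Grade 3 thrombocytopenia and clinically significant bleeding before the Day 29 doses therefore has a DLT and also cannot complete.

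**Working it through.** The documents state no DLT rate and no operating characteristic for Phase I, so there is no figure to reproduce and no probability is given here. The check is on the logic of the rules, assuming no landmark AE.

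**Part (a): counting unit.** Let *k* be the number of the six patients with at least one DLT, and *d* the total number of DLTs. The protocol de-escalates if *k* ≥ 2. The SAP, as worded, de-escalates if *d* ≥ 2.

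| *k* | *d* | Protocol | SAP |
|---|---|---|---|
| 0 | 0 | proceed | proceed |
| 1 | 1 | proceed | proceed |
| 1 | 2 or more | proceed | **de-escalate** |
| 2 or more | 2 or more | de-escalate | de-escalate |

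Since *d* ≥ *k*, no other row is possible. The rules part only when exactly one patient has two or more DLTs, and the SAP is then the more cautious. As a check, allow 0, 1 or 2 DLTs per patient. There are 3^6 = 729 patterns, and the rules disagree in 6 of them: one patient with two, the other five with none. This counts patterns and is not a probability.

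An example is one patient with Grade 4 thrombocytopenia plus Grade 3 neutropenia lasting more than 7 days. Both fall under DLT criterion 6. Neither is a landmark AE, provided they are not judged immune-related, because landmark AEs cover liver enzymes, liver function, immune-related events and skin lesions.

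**Part (b): evaluability, side by side.**

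| Place | Patient stopped by a DLT before Day 29 |
|---|---|
| Protocol Definitions table | not evaluable |
| Protocol 12.6 | not evaluable, so not in the DLT population |
| Protocol 6.6.2 | evaluable |
| Protocol 10.1, DLT period | kept by implication: only withdrawals for reasons other than toxicity are replaced (though the same paragraph describes evaluable patients as having had all five administrations) |
| SAP 2.3 and 6.1 | evaluable, in the DLT population |
| Protocol 12.5 (per protocol analyses) | major deviation, replace |
| SAP 6.2 | not a deviation |

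Worked case: patient A is stopped before Day 29 by Grade 3 thrombocytopenia with bleeding, patient B completes with a DLT, patients C to F have none, and patient G is a DLT-free replacement.

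- First six treated (A to F): 2 of 6 with a DLT, de-escalate.
- Completers only (B to G): 1 of 6, proceed.
- SAP 6.1 set (A to F, with A kept and no replacement needed): 2 of 6, de-escalate.

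**The case against.** The best case against giving this much weight has five parts.

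1. *Case (b) does not follow from an operating rule.* The protocol trigger refers to the first six patients, not to the DLT population. Only SAP 6 ties a DLT population to the decision, and the SAP's version keeps DLT patients. This stands: case (b) changes the decision only if someone applies the protocol's version of the set. What remains is two different sets under one name.
2. *Case (a) is narrow.* Liver DLTs largely drop out. Entry requires AST and ALT at or below 5 times ULN, so reaching 10 times ULN is at least a doubling, and a doubling from baseline is a landmark AE that de-escalates under both documents. Immune-related DLTs also overlap with the landmark terms. This stands too. The remaining cases are mainly non-hepatic and not immune-related, such as haematological DLTs.
3. *The count is not final.* Under protocol 6.2 the ISC recommendation prevails, and under 14.4 no new cohort starts without its advice. True, but the ISC still needs one written rule to start from.
4. *Version gap.* SAP 1 cites the protocol of 22 December 2017, while the protocol at hand is the amended version of 20 March 2019. This might explain how (a) arose. It does not remove the present mismatch, and it cannot explain (b), where the protocol contradicts itself.
5. *Probably too late.* Protocol 3.1.3 planned Phase I recruitment to end by January 2018, and SAP version 3 is dated 12 December 2018. The documents do not say when the decision was taken. If it was already taken, rewording would change no dosing, and the record of what was done becomes the useful part.

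The SAP's wording may also be loose shorthand for patients. If so, it should say patients, since it appears in two sections and in both directions.

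**Conclusion.** The concern holds on both parts, as a conflict between written rules rather than an absence of safety review. In (a), the decision flips when exactly one patient has two or more DLTs and no landmark AE occurs in any patient; the SAP then errs on the safe side. In (b), the completers-only wording is wrong for its purpose, but it alters the decision only if the protocol's DLT set is used in place of the SAP's. No claim is made about how often either would happen, because that would require DLT rates the documents do not give. Sample size, alpha and power for Phase IIa are unaffected. It should be corrected, but it does not undermine the trial.

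**What to change.** - **SAP 2.1 and 7.2:** state the trigger as a DLT in more than one patient, and the condition to proceed as a DLT in no more than one patient.
- **Protocol Definitions table and 12.6:** extend the Phase I evaluable definition to patients who had a DLT, as protocol 6.6.2 and SAP 2.3 already do.
- **Protocol 12.5:** limit the Phase I non-completion deviation to patients without a DLT, as SAP 6.2 already does.
- **If the Phase I decision has been made:** record in the SAP and study report which counting unit and which patient set were applied.

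The cost is wording in two SAP sections and three places in the protocol; the protocol edits go through the signed amendment route in 13.1. No new data are needed, because the AE overview table in SAP 8.8.1.4 already reports both patients and events for DLTs.
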